The hypothesis is that Filtek™ Bulk Fill Posterior Restorative composite resin, when used to restore posterior teeth, will exhibit similar clinical performance – in terms of wear resistance, marginal integrity, durability, and other clinical characteristics – to Filtek™ Supreme Ultra Universal Restorative composite resin, a restorative material in everyday use in dentistry.

STUDY OBJECTIVES

The purpose of this study is to compare the clinical performance of Filtek™ Bulk Fill Posterior Restorative with a commercially available conventional composite resin restorative material when used to restore Class II preparations in molar and premolar teeth.

STUDY DESIGN

The study design is a randomized, controlled, comparative effectiveness clinical trial investigation of the test materials used to restore moderate-sized Class II cavities in posterior permanent teeth in adult dental patients. The study will be of five years duration.

Primary outcome measures

The primary endpoint is the clinical performance of the restorations measured according to the rating system published by Hickel et al. [16].

In the past, USPHS (or Ryge) criteria have been used to evaluate the clinical performance of restorative materials. These criteria were developed as a standardized method to clinically evaluate the quality of an amalgam or resin restoration shortly after placement. The word “quality” means the degree of excellence or degree of conformance to a standard. The rating system is based on an operational approach to quality assessment, which a dentist would use when examining any restoration in the mouth of a new patient. The dentist must decide whether to retain or replace the restoration [17].

This rating system has been in use for over 30 years of clinical investigation. Because the clinical performance of restorative materials has continuously improved, the original Ryge criteria have been modified frequently, which makes it difficult to compare studies on modern restorative materials.

Hickel et al. have offered a new approach to controlled clinical studies of restorative materials. Their publication deals with, among other issues, an adaptation of the established Ryge-criteria of restorative materials [16]. With this rating system, which will be used in this

study, restorations are evaluated scoring for their esthetic, functional and biologic properties.

Secondary outcome measures

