- Have xerostomia caused by medications, Sjögren's syndrome, etc.
- Are individuals with special needs.

Distribution of restorations

Each subject shall have a minimum of one pair and a maximum of two pairs of permanent molar or premolar teeth requiring moderate sized Class II restorations. No tooth shall require more than one restoration. Sufficient subjects will be recruited to ensure 50 pairs of test and control study restorations are placed. Although desirable, the pairs are not required to be precisely matched. For example, for purposes of the study, paired restorations can be placed in teeth #15 and #31 (upper left second molar and lower right second molar).

All teeth and restorations in the study will have occlusal contacts. All restorations, with the exception of disto-occlusal restorations in the most distal molars, will have a proximal contact with the adjacent tooth. No two test restorations of either material will be in occlusal or proximal contact with each other.

Selection of Teeth

In addition to the above criteria, the following will apply in tooth selection:

- The tooth must be vital, as determined by thermal test (Hygenic Endo-Ice, Coltène/Whaledent AG).
- The tooth must be of typical size, appearance and morphology.
- The tooth must share, where appropriate, sound proximal contacts with adjacent teeth.
- The tooth must be free of cracks and other defects and lesions necessitating operative intervention other than the restoration to be undertaken as part of the study.
- Proper isolation must be possible.

MATERIALS

The test material is Filtek™ Bulk Fill Posterior Restorative, a bulk fill, low-shrink, light-cured, radiopaque composite resin restorative indicated for use in direct posterior situations. The control material is Filtek™ Supreme Ultra Universal Restorative, a conventional composite resin. Restorations will be bonded with Scotchbond Universal Adhesive.

Manufacturers' instructions for use will be followed for all restoration placements included in the study. Manufacturers' instructions for use for Filtek™ Supreme Ultra Universal Restorative and Filtek™ Bulk Fill Posterior Restorative, and Scotchbond Universal Adhesive are given in the Investigator's Brochure.

PRE-OPERATIVE PROCEDURES

In the screening visit, written informed consent will be obtained from each subject. Each subject will be allowed to ask questions concerning the evaluation and to consider the answers given before signing the consent form.

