The pre-operative status and a periapical radiograph (where clinically indicated) of each tooth to be included in the study will be evaluated and a pre-treatment status form will be completed (Patient Registration Form). The condition of the gingival tissue adjacent to each tooth to be restored will be assessed (four sites: facial, lingual, mesial and distal) and recorded as pre-treatment measurements (Patient Registration Form). Oral hygiene status including plaque index will be determined after periodontal evaluation. Appropriate vitality and radiographic assessments will be completed where indicated clinically, and will be recorded. A pre-operative photographic record will be made.

The restorative material to be used will be allocated by means of a randomization scheme based on computer generated random numbers (Appendix 1). Before starting the study, the PI will decide, by means of a toss of a coin, whether even or odd numbers indicate the test or control treatment. For each set of paired teeth, the lowest numbered tooth (Universal Numbering System) will be selected first. Before cavity preparation, the first randomization number in the sequence will be noted and the allocated treatment procedure carried out as indicated by the random number obtained. The second cavity is then prepared and restored using the second treatment option (next number in the row). Restorative treatments will be randomly assigned to the study teeth at the same visit at which pre-treatment gingival condition, vitality, etc., are determined.

The treating clinician will complete the preparation and placement of restorations, and the arrangements for the subsequent follow-up of the patients.

OPERATIVE PROCEDURES

Local anesthesia will be administered unless declined by the patient. The teeth to be restored will be prepared using conventional instruments and techniques, and no bevels will be placed on any of the cavosurface margins. Shades will be selected before the procedure is started and the tooth is still moist. Rubber dam will be used.

A sectional metal matrix (Garrison Dental or similar) and bitine ring will be placed along with plastic or wooden wedges. At the operator's discretion (e.g., if the preparation is

too wide for a sectional matrix), a thin circumferential metal matrix (Convexi-T, Clinician's Choice or similar) may be used. The bonding system will be used in the selective etch mode according to manufacturer's instructions.

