All restorations carried out in this study will be at no cost to the subjects. Subjects will be expected to attend the one-, two-, three-, and five-year follow up visits. Compensation of \$50 will be paid to each subject at baseline and each follow-up visit (total of \$250).

MONITORING

The study will be monitored at appropriate intervals by [name], Scientific Affairs Manager, 3M ESPE Dental Products, [name] [[contact]], or his designee, by means of regular contact to evaluate study data and photographs.

DATABASE MANAGEMENT

Each subject recruited into the study will be given a unique identifying code number and the subject's identity will be kept confidential as far as is practical.

ANALYSIS OF THE RESULTS

The demographic and baseline measurements, and the study data obtained, will be analyzed by means of tables of percentages to summarize the characteristics of the patients and the baseline data. Tables of percentages will be prepared to illustrate the follow-up and retrospective analysis findings. Cross tabulation will be prepared as necessary.

Statistical analyses

Chi-square (χ^2), McNemar and Mann-Whitney-U tests will be applied as appropriate to compare the baseline and follow-up/review findings regarding the two types of restorations.

PROBLEM CASES

In the case of an experimental Filtek™ Bulk Fill Posterior Restorative or Filtek™ Supreme Ultra Universal Restorative composite resin restoration being found to have failed or to be clinically unsatisfactory on review, the investigator will:

- Complete the failed restoration form.
- Make a photographic and silicone impression record of the failed restoration.
- Make arrangements to replace or, if appropriate, repair the restoration.

Replacements of failed restorations will not form part of the study.

In the case of failure of restorations placed using either restorative system, the tooth will be re-restored at no cost to the subject or investigator. The contact person at 3M ESPE ([name], [contact]) should be notified before this treatment is done.

ADVERSE EVENTS

If an adverse event occurs any decision as to whether to prematurely stop the study will be taken jointly by the PI, 3M ESPE, and IRB. Changes to the protocol will be by arrangement between the PI, IRB, and 3M ESPE, and will take the form of a signed amendment.

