3. Clinically sufficient / satisfactory (minor shortcomings, no unacceptable effects but not adjustable without damage to the tooth)	5.3. Two or more or larger hairline cracks and / or chipping (not affecting the marginal integrity or proximal contact).	6.3.1. Gap < 150 µm not removable. 6.3.2. Several small enamel or dentin fractures.	7.3. Differing wear rate to enamel but within the biological variation (< 50 % or 150-300 % of corresponding enamel).	8.3. Slightly too weak, no indication of damage to tooth, gingiva or periodontal structures (50 µm metal blade can pass easily but not 100 µm).	9.3. 1. Marginal gap < 200 µm. 9.3. 2. Negative steps visible < 250 µm. No adverse effects noticed. 9.3.3. Poor radiopacity of filling material.	10.3. Minor criticism of aesthetics. 10.3.1. Aesthetic shortcomings. 10.3.2. Some lack of chewing comfort. 10.3.3. Time consuming procedure and / or similar. No adverse clinical effects.
4. Clinically unsatisfactory (but repairable)	5.4. Chipping that damage marginal quality or proximal contacts, bulk	6.4.1. Gap > 250 µm or dentin / base exposed.	7.4. Wear considerably exceeds normal enamel wear, or occlusal contact	8.4. Too weak (100 µm metal blade can pass) and possible damage (food	9.4.1. Marginal gap > 250 µm. 9.4.2. Excess accessible but not removable.	10.4. Desire for improvement (reshaping of anatomic

	fractures with or without partial loss (less than half of the restoration).	6.4.2. Chipping damaging margins. 6.4.3. Notable enamel or dentin wall fracture.	points are lost (restoration > 300 % of enamel wear or antagonist > 300 %).	impaction). Repair possible.	9.4.3. Negative steps > 250 µm and repairable.	form or refurbishing, etc.).
5. Clinically poor (replacement necessary)	5.5. (Partial or complete) loss of restoration.	6.5. Filling is loose but in situ.	7.5. Wear is excessive (restoration or antagonist > 500 % of corresponding enamel).	8.5. Too weak and / or clear damage (food impaction) and / or pain / gingivitis. Requires replacement.	9.5.1. Secondary caries, large gaps. 9.5.2. Apical pathology. 9.5.3. Fracture / loss of restoration or tooth.	10.5. Completely dissatisfied and / or adverse effects including pain.

c) Biological properties	11. Postoperative (hyper) sensitivity and tooth vitality	12. Recurrence of caries, erosion, abfraction	13. Tooth integrity (enamel cracks)	14. Periodontal response (always compared to a reference tooth)	15. Adjacent mucosa	16. Oral and general health

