
4. Clinically unsatisfactory (repair for prophylactic reasons)
	
11.4.1. Premature / very intense. 11.4.2. Extremely delayed / weak with subjective complaints. 11.4.3. Negative sensitivity. Intervention necessary but not replacement.
	
12.4.1. Caries with cavitation. 12.4.2. Erosion in dentin. 12.4.3. Abrasion / abfraction in dentin. Localized and accessible and can be repaired.
	
13.4.1. Major enamel split (gap > 250 µm or dentin or base exposed). 13.4.2. Crack > 250 µm (probe penetrates).
	
14.4.1. Plaque accumulation not acceptable. 14.4.2. Gingival bleeding not acceptable. 14.4.3. Pocket depth increase > 1 mm.
	
15.4. Suspected mild allergic, lichenoid, or toxicological reaction.
	
16.4. Persisting local or general symptoms of oral contact stomatitis, lichen planus, or allergic reactions (or remitting). Intervention necessary but no replacement.

5. Clinically poor (replacement necessary)
	
11.5. Very intense, acute pulpitis or non-vital. Endodontic treatment is necessary and restoration has to be replaced.
	
12.5. Deep secondary caries or exposed dentin that is not accessible for repair of restoration.
	
13.5. Cusp or tooth fracture.
	
14.5. Severe / acute gingivitis or periodontitis.
	
15.5. Suspected severe allergic, lichenoid, or toxicological reaction.
	
16.5. Acute / severe local and / or general symptoms.

APPENDIX 1

**Clinical investigation of a new bulk fill composite resin
in the restoration of posterior teeth**

RANDOM NUMBERS TABLE

30	89	34	43	98	79	50	49
98	07	53	64	54	23	87	50
91	54	58	41	06	79	69	90
13	38	59	44	46	25	38	19
65	48	27	62	58	51	79	30
78	05	73	70	42	19	74	41
75	26	79	66	12	05	88	07
15	62	76	89	23	14	38	65
63	40	79	60	02	89	31	50
10	55	17	44	07	76	62	37
05	34	19	54	27	96	52	47
27	70	88	07	10	45	77	28
71	66	24	27	16	73	03	98
43	04	83	14	13	96	53	98
65	28	89	34	06	75	17	70
51	46	21	60	13	84	32	47
06	71	33	46	59	78	29	16
21	82	98	23	75	90	10	63
69	01	90	21	57	14	98	64
92	43	88	01	29	12	45	58
16	81	70	31	43	02	93	10
35	12	65	24	50	71	43	04
72	79	96	25	39	14	21	88
20	31	03	98	60	51	93	62
89	68	51	28	99	30	67	48
46	81	92	79	93	02	71	26
19	98	34	59	48	29	03	22
46	93	59	42	41	42	13	74
07	30	41	50	11	80	23	78
06	22	74	23	59	70	18	05
36	97	60	89	07	24	48	17
06	31	70	27	37	18	53	94
05	08	53	09	70	88	63	02
20	82	16	77	29	58	37	50
17	60	07	20	21	10	90	13
94	09	87	30	12	53	62	91
31	26	50	29	52	19	41	98
70	07	17	36	92	21	14	29
81	18	51	12	67	04	21	72

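### Pre-treatment gingival condition is recorded on every study tooth, but the planned tests do not adjust the periodontal-response comparison for it, so some precision may be forgone

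*Combined protocol and SAP*

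**What the plan says.** The protocol's Pre-operative Procedures section says: "The condition of the gingival tissue adjacent to each tooth to be restored will be assessed (four sites: facial, lingual, mesial and distal" and so on, with the results kept as pre-treatment measurements on the Patient Registration Form. It adds: "Oral hygiene status including plaque index will be determined after periodontal evaluation".

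The matching follow-up item is in Table 1, part c: "14. Periodontal response (always compared to a reference tooth". It is scored 1 to 5 on plaque, inflammation or bleeding, and pockets. It belongs to the primary rating system (Primary outcome measures): "The primary endpoint is the clinical performance of the restorations measured according to the rating system published by" the cited recommendations.

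Under Analysis of the Results, baseline data go into "tables of percentages to summarize the characteristics of the patients and the baseline data". The Statistical analyses paragraph names the chi-square test and then says: "McNemar and Mann-Whitney-U tests will be applied as appropriate to compare the baseline and follow-up/review findings regarding the two types of restorations". It names no regression model, covariate or stratified test. On numbers, Distribution of restorations says: "Sufficient subjects will be recruited to ensure 50 pairs of test and control study restorations are placed".

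**The concern.** Criterion 14 is the follow-up counterpart of the pre-treatment gingival record. A paired comparison of follow-up scores removes what the two teeth in one mouth share. It does not remove a difference in starting condition between them. Such differences are plausible: pairs need not be closely matched, the protocol's own example puts the two teeth in opposite jaws and on opposite sides, and both new lesions and failed restorations are eligible.

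Any part of that starting difference that persists to follow-up adds noise to the material contrast. With 50 pairs, or about 40 if retention falls to the guideline minimum, a baseline reading that predicts the outcome could narrow the interval at almost no cost. The readings precede placement, so the material cannot have affected them.

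**Working it through.** **Plan's own figure.** There is none to reproduce. The 50 pairs, and the 40 restorations at 18 months, rest on a guideline minimum. The documents give no alpha, power, effect size, standard deviation or baseline–outcome correlation.

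**What the named tests do.** Chi-square and Mann-Whitney U compare two sets of scores. McNemar compares paired binary results. None includes a covariate. A Mann-Whitney U on change from baseline would use the baseline, but the plan does not specify it. It would also need the four-site record and the 1–5 score to share a scale, which is not shown. The variance factor for change is 2(1 − r), so it helps only if r exceeds 0.5.

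**Normal-theory calculation.** Assumptions: two-sided 5% level, one pair per subject, and rho as the correlation between within-pair baseline and follow-up differences.

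- Variance factor after adjustment: 1 − rho².
- Equivalent number of pairs: n / (1 − rho²).
- Power: noncentral t, unadjusted with n − 1 degrees of freedom, adjusted with n − 2 and standardised effect d/√(1 − rho²). The effect giving 80% unadjusted power is d = 0.404 for 50 pairs and 0.454 for 40. Adjusted power is nearly the same for both.

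| rho | 1 − rho² | 50 pairs count as | 40 pairs count as | Power, from 80% |
|---|---|---|---|---|
| 0.2 | 0.96 | 52.1 | 41.7 | 81.5% |
| 0.3 | 0.91 | 54.9 | 44.0 | 83.5% |
| 0.4 | 0.84 | 59.5 | 47.6 | 86.3% |
| 0.5 | 0.75 | 66.7 | 53.3 | 90% |
| 0.6 | 0.64 | 78.1 | 62.5 | 94% |

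From 60% unadjusted power, rho 0.5 gives 72%.

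**Cost of estimating the slope.** The table leaves this out. For normally distributed baseline differences it multiplies the variance by (n − 2)/(n − 3), which is 48/47 = 1.021 at 50 pairs. At rho 0.2 the net factor is 0.96 × 1.021 = 0.98, which is close to no gain. At rho 0 it is 1.021, a small loss. Simulation with 1–5 scores agrees: at rho 0, power went from 0.755 to 0.743 (50 pairs) and from 0.652 to 0.645 (40 pairs).

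**Sparse scores.** Simulation of 50 pairs (6,000 runs; assumed latent shift 0.6, subject share of variance 0.4, baseline cut to 0–3), unadjusted against adjusted within-pair difference:

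| Control teeth scoring 1 | rho | Unadjusted | Adjusted |
|---|---|---|---|
| 90% | 0.2 | 0.578 | 0.563 |
| 90% | 0.3 | 0.584 | 0.583 |
| 90% | 0.5 | 0.580 | 0.609 |
| 80% | 0.5 | 0.762 | 0.806 |

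A separate run with 80–90% of control teeth scoring 1 gave about 2.5 to 4 points at rho 0.5 and nothing at rho 0.2. The gain is smaller than in the normal-theory table because rho is set on the underlying scale, and cutting to few categories weakens the correlation between the observed differences.

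**Error rate.** With no material effect, the unadjusted analysis in the sparse-score simulation rejected in 3.9% to 4.9% of runs.

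**The case against.** The strongest case against is that the benefit cannot be verified and is probably small. Most of it stands.

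- **Rho may be low.** The state shared by both teeth already cancels in a paired analysis. A difference caused by a failed restoration or a lesion is treated at placement, one to five years before criterion 14 is scored.
- **Criterion 14 is partly referenced already.** It is scored against a reference tooth, and one score-4 descriptor is itself a change: "14.4.3. Pocket depth increase > 1 mm". This reduces the scope for gain without removing it. A reference tooth is not the study tooth's own starting state, and scores 1 to 3 mainly describe current levels.
- **The target is narrow.** Criterion 14 is one of 16 and none is singled out. The hypothesis names wear resistance, marginal integrity and durability, and covers the rest only as other characteristics.
- **Other choices usually matter more.** In a simulation of 50 pairs (latent shift 0.4 SD, subject share 0.3), an unpaired Mann-Whitney U had power 0.42–0.45 and McNemar on a dichotomised score 0.28–0.30, against 0.55–0.56 for a paired, unadjusted score comparison. Adjustment then added 0.05 at r = 0.4 and 0.11 at r = 0.6. This does not count against the fix, which also makes the analysis paired.

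A reader might also infer that a chance imbalance in starting inflammation could pass for a material effect, so that the plan is biased. The documents do not support that. Material is allocated at random within each pair, so such imbalance is already inside the nominal error rate.

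**Conclusion.** The point holds as an optional, low-cost improvement. A tooth-level baseline is collected and, as planned, the criterion 14 comparison is not adjusted for it.

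From 80% power the normal-theory gain is about 4 points at rho 0.3 and 10 at rho 0.5, before roughly one point for estimating the slope. With 80–90% of teeth scoring 1 it is about 2.5 to 4 points at rho 0.5. At rho 0.2 or below it is about nil, and at rho 0 about one point is lost.

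A reader might conclude that precision is definitely being lost. The documents do not show this: they give neither rho nor the expected score distribution. All sizes above rest on assumed values of these, on one pair per subject, and on a paired unadjusted comparison as the starting point, which the plan does not commit to.

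**What to change.** Add to the Statistical analyses paragraph: for criterion 14 at each review, the within-pair difference in score (test minus control) is regressed on the within-pair difference in the pre-treatment gingival reading. The intercept is the material effect, and standard errors are clustered on subject where a subject contributes two pairs.

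State in advance how the four sites are summarised, on the scale used on the Patient Registration Form. That scale is not shown in the documents, so it should be confirmed before a summary such as a mean is chosen.

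A proportional-odds model clustered on subject may be added if scores are not sparse; the figures here were not derived for that model. Keep the unadjusted tables and tests alongside. Do not adjust for readings taken after placement, because the material can affect them.

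Cost: a short addition to the analysis text and one extra model per review, with no new visit, procedure or subject. The downside is one degree of freedom and about one point of power if the baseline is uninformative.

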3. Clinically sufficient / satisfactory (minor shortcomings, no unacceptable effects but not adjustable without damage to the tooth)	1.3. Dull surface but acceptable if covered with film of saliva.	2.3. Moderate surface staining, also present on other teeth, not aesthetically unacceptable.	3.3. Clear deviation but acceptable. Does not affect aesthetics. 3.3.1. More opaque. 3.3.2. More translucent. 3.3.3. Darker. 3.3.4. Brighter.	4.3. Form differs but is not aesthetically displeasing.
4. Clinically unsatisfactory (but repairable)	1.4. Rough surface, cannot be masked by saliva film, simple polishing is not sufficient. Further intervention necessary.	2.4. Surface staining present on the restoration and is unacceptable. Major intervention necessary for improvement.	3.4. (Localized) clinically unsatisfactory but can be corrected by repair. 3.4.1. Too opaque. 3.4.2. Too translucent. 3.4.3. Too dark. 3.4.4. Too bright.	4.4. Form is affected and unacceptable aesthetically. Intervention (correction) necessary.
5. Clinically poor (replacement necessary)	1.5. Quite rough, unacceptable plaque, retentive surface.	2.5. Severe staining and / or subsurface staining (generalized or localized), not accessible for intervention.	3.5. Unacceptable. Replacement necessary.	4.5. Form is completely unsatisfactory and / or lost. Repair not feasible / reasonable, replacement needed.

b) Functional properties	5. Fractures and retention	6. Marginal adaptation	7. Wear	8. Contact point / food impact	9. Radiographic examination (when applicable)	10. Patient's view
1. Clinically excellent / very good	5.1. Restoration retained, no fractures / cracks.	6.1. Harmonious outline, no gaps, no discoloration.	7.1. Physiological wear equivalent to enamel (80-120% of corresponding enamel).	8.1. Normal contact point (floss or 25 µm metal blade can be inserted but not 50 µm blade).	9.1. No pathology, harmonious transition between restoration and tooth.	10.1. Entirely satisfied.
2. Clinically good (very good after polishing)	5.2. Small hairline crack.	6.2.1. Marginal gap (50 µm). 6.2.2. Small marginal fracture removable by polishing.	7.2. Normal wear with only slight difference to enamel (50-80 % or 120-150 % of corresponding enamel).	8.2. Slightly too strong but no disadvantage.	9.2.1. Acceptable excess present. 9.2.2. Positive / negative step present at margin < 150 µm.	10.2. Satisfied.
3. Clinically sufficient / satisfactory (minor shortcomings, no unacceptable effects but not adjustable without damage to the tooth)	5.3. Two or more or larger hairline cracks and / or chipping (not affecting the marginal integrity or proximal contact).	6.3.1. Gap < 150 µm not removable. 6.3.2. Several small enamel or dentin fractures.	7.3. Differing wear rate to enamel but within the biological variation (< 50 % or 150-300 % of corresponding enamel).	8.3. Slightly too weak, no indication of damage to tooth, gingiva or periodontal structures (50 µm metal blade can pass easily but not 100 µm).	9.3. 1. Marginal gap < 200 µm. 9.3. 2. Negative steps visible < 250 µm. No adverse effects noticed. 9.3.3. Poor radiopacity of filling material.	10.3. Minor criticism of aesthetics. 10.3.1. Aesthetic shortcomings. 10.3.2. Some lack of chewing comfort. 10.3.3. Time consuming procedure and / or similar. No adverse clinical effects.
4. Clinically unsatisfactory (but repairable)	5.4. Chipping that damage marginal quality or proximal contacts, bulk	6.4.1. Gap > 250 µm or dentin / base exposed.	7.4. Wear considerably exceeds normal enamel wear, or occlusal contact	8.4. Too weak (100 µm metal blade can pass) and possible damage (food	9.4.1. Marginal gap > 250 µm. 9.4.2. Excess accessible but not removable.	10.4. Desire for improvement (reshaping of anatomic

	fractures with or without partial loss (less than half of the restoration).	6.4.2. Chipping damaging margins. 6.4.3. Notable enamel or dentin wall fracture.	points are lost (restoration > 300 % of enamel wear or antagonist > 300 %).	impaction). Repair possible.	9.4.3. Negative steps > 250 µm and repairable.	form or refurbishing, etc.).
5. Clinically poor (replacement necessary)	5.5. (Partial or complete) loss of restoration.	6.5. Filling is loose but in situ.	7.5. Wear is excessive (restoration or antagonist > 500 % of corresponding enamel).	8.5. Too weak and / or clear damage (food impaction) and / or pain / gingivitis. Requires replacement.	9.5.1. Secondary caries, large gaps. 9.5.2. Apical pathology. 9.5.3. Fracture / loss of restoration or tooth.	10.5. Completely dissatisfied and / or adverse effects including pain.

c) Biological properties	11. Postoperative (hyper) sensitivity and tooth vitality	12. Recurrence of caries, erosion, abfraction	13. Tooth integrity (enamel cracks)	14. Periodontal response (always compared to a reference tooth)	15. Adjacent mucosa	16. Oral and general health
1. Clinically very good	11.1. No hypersensitivity, normal vitality.	12.1. No secondary or primary caries.	13.1. Complete integrity.	14.1. No plaque, no inflammation, no pockets.	15.1. Healthy mucosa adjacent to restoration.	16.1. No oral or general symptoms.
2. Clinically good (after correction very good)	11.2. Low hypersensitivity for a limited period of time, normal vitality.	12.2. Very small and localized areas of: 1. Demineralization, 2. Erosion, or 3. Abfraction. No operative treatment required.	13.2.1. Small marginal enamel split (< 150 µm). 13.2.2. Hairline crack in enamel (< 150 µm not probable).	14.2. Little plaque, no inflammation (gingivitis), no pocket development.	15.2. Healthy after minor removal of mechanical irritations (sharp edges, etc.).	16.2. Minor transient symptoms of short duration (of known or unknown origin) local or generalized.
		12.3. Larger areas of:				

3. Clinically sufficient / satisfactory (minor shortcomings with no adverse effects but not adjustable without damage to the tooth)
	
11.3.1. Premature / slightly more intense. 11.3.2. Delayed / weak sensitivity. No subjective complaints, no treatment needed.
	
1. Demineralization, 2. Erosion, or 3. Abrasion / abfraction. Only preventive measures necessary (dentin not exposed).
	
13.3.1. Enamel split < 250 µm. 13.3.2. Crack < 250 µm. No adverse effects.
	
14.3.1. Plaque accumulation at acceptable level. 14.3.2. Gingival bleeding acceptable. 14.3.3. Pocket formation acceptable.
	
15.3. Alteration of mucosa but no suspicion of causal relationship with filling material.
	
16.3. Transient symptoms, local and / or general.


4. Clinically unsatisfactory (repair for prophylactic reasons)
	
11.4.1. Premature / very intense. 11.4.2. Extremely delayed / weak with subjective complaints. 11.4.3. Negative sensitivity. Intervention necessary but not replacement.
	
12.4.1. Caries with cavitation. 12.4.2. Erosion in dentin. 12.4.3. Abrasion / abfraction in dentin. Localized and accessible and can be repaired.
	
13.4.1. Major enamel split (gap > 250 µm or dentin or base exposed). 13.4.2. Crack > 250 µm (probe penetrates).
	
14.4.1. Plaque accumulation not acceptable. 14.4.2. Gingival bleeding not acceptable. 14.4.3. Pocket depth increase > 1 mm.
	
15.4. Suspected mild allergic, lichenoid, or toxicological reaction.
	
16.4. Persisting local or general symptoms of oral contact stomatitis, lichen planus, or allergic reactions (or remitting). Intervention necessary but no replacement.

5. Clinically poor (replacement necessary)
	
11.5. Very intense, acute pulpitis or non-vital. Endodontic treatment is necessary and restoration has to be replaced.
	
12.5. Deep secondary caries or exposed dentin that is not accessible for repair of restoration.
	
13.5. Cusp or tooth fracture.
	
14.5. Severe / acute gingivitis or periodontitis.
	
15.5. Suspected severe allergic, lichenoid, or toxicological reaction.
	
16.5. Acute / severe local and / or general symptoms.

APPENDIX 1

**Clinical investigation of a new bulk fill composite resin
in the restoration of posterior teeth**

RANDOM NUMBERS TABLE

30	89	34	43	98	79	50	49
98	07	53	64	54	23	87	50
91	54	58	41	06	79	69	90
13	38	59	44	46	25	38	19
65	48	27	62	58	51	79	30
78	05	73	70	42	19	74	41
75	26	79	66	12	05	88	07
15	62	76	89	23	14	38	65
63	40	79	60	02	89	31	50
10	55	17	44	07	76	62	37
05	34	19	54	27	96	52	47
27	70	88	07	10	45	77	28
71	66	24	27	16	73	03	98
43	04	83	14	13	96	53	98
65	28	89	34	06	75	17	70
51	46	21	60	13	84	32	47
06	71	33	46	59	78	29	16
21	82	98	23	75	90	10	63
69	01	90	21	57	14	98	64
92	43	88	01	29	12	45	58
16	81	70	31	43	02	93	10
35	12	65	24	50	71	43	04
72	79	96	25	39	14	21	88
20	31	03	98	60	51	93	62
89	68	51	28	99	30	67	48
46	81	92	79	93	02	71	26
19	98	34	59	48	29	03	22
46	93	59	42	41	42	13	74
07	30	41	50	11	80	23	78
06	22	74	23	59	70	18	05
36	97	60	89	07	24	48	17
06	31	70	27	37	18	53	94
05	08	53	09	70	88	63	02
20	82	16	77	29	58	37	50
17	60	07	20	21	10	90	13
94	09	87	30	12	53	62	91
31	26	50	29	52	19	41	98
70	07	17	36	92	21	14	29
81	18	51	12	67	04	21	72
